### 8.3 Annual safety report

In addition to the expedited reporting of severe ADEs, the sponsor will submit, once a year throughout the clinical trial, a safety report to the accredited METC, competent authority, and competent authorities of the concerned Member States.

This safety report consists of:

- a list of all suspected (unexpected or expected) severe adverse device events, along with an aggregated summary table of all reported serious adverse reactions, ordered by organ system, per study

- a report concerning the safety of the subjects, consisting of a complete safety analysis and an evaluation of the balance between the efficacy and the harmfulness of the medicine under investigation.

#### **8.4 Follow-up of adverse events**

All AEs as defined in section 8.2.1 will be followed until they have abated, or until a stable situation has been reached. Depending on the event, follow up may require additional tests or medical procedures as indicated, and/or referral to the general physician or a medical specialist.

SAEs as defined in section 8.2.2 need to be reported till end of study within the Netherlands, as defined in the protocol.

#### **8.5 Data Safety Monitoring Board (DSMB) / Safety Committee**

A DSMB is not needed given the very low risk of the study.

## 9. STATISTICAL ANALYSIS

### 9.1 Statistical analysis

To analyse the data, a two-group comparison of proportions will be performed using appropriate statistical tests, such as the chi-square test or Fisher's exact test. The null hypothesis ( $H_0$ ) assumes no difference in completeness rates between the manual urine monitor and the FlowSure device, while the alternative hypothesis ( $H_a$ ) posits a significant difference in completeness rates. The resulting p-value will provide an assessment of the statistical significance of the observed difference.

Additionally, further exploratory analyses, such as subgroup analyses or regression modelling, may be conducted to investigate potential factors influencing completeness rates and to account for confounding variables.

The statistical software R and Rstudio will be utilized for data analysis, and a significance level of 0.05 will be used to determine statistical significance. The findings will be interpreted in conjunction with clinical considerations to guide conclusions regarding the comparative completeness of hourly urine production registration between the manual urine monitor and the FlowSure device.

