## 2. OBJECTIVES

The objective of the study is in part A of the study protocol to demonstrate that in clinical care the investigational FlowSure device is able to monitor urine production accurately and safely. The aim in part B of the study is to demonstrate that the use of the investigational FlowSure device will result in more complete and (cost effective) urine production registration.

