### 3. STUDY DESIGN

The study will consist of two parts. Part A is single arm intervention study in which patients will receive both the manual monitors and automated FlowSure monitor (both devices will be used in conjunction). Part B is a two-arm randomized non-blinded intervention study in which patients will be monitored with either the manual monitoring or automated FlowSure monitoring.

In both part A and part B the study will last for duration that the patient has a urine catheter inserted with a maximum of 24 hours. The setting of the study will be hospitalized patients who - for medical reasons unrelated to the study - have a urine catheter inserted.

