### 7.1 Study parameters/endpoints

#### 7.1.1 Main study parameter/endpoint

The primary outcome event in Part A will be the accuracy of urine measurement over two set time intervals (a nursing shift of 8 hours and a full 24-hours period) using manual monitoring and automated monitoring. The golden standard is the total urine production measured in a measuring cup by draining the collection bag in comparison with the new FlowSure device. The primary outcome in part B of the study will be the completeness of the hourly diuresis registration will be compared between the manual and automated measurement groups.

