### 9.2 Primary study parameter(s)

The primary outcome parameter of this study is the completeness of hourly urine production registration. It refers to the extent to which the two devices, the manual urine monitor and the FlowSure device, accurately capture and record hourly urine production data over a 24-hour period.

Completeness of hourly urine production registration represents the proportion or percentage of the total hourly measurements that are successfully recorded by each device.

For example, if a patient's urine output is measured every hour for 24 hours, the completeness rate indicates how many of these hourly measurements are successfully captured by the device.

In this study, the primary objective is to compare the completeness of hourly urine production registration between the manual urine monitor and the FlowSure device as registered in the electronic health record. The manual urine monitor has an assumed completeness rate of approximately 50% of hourly registrations, while Device B (FlowSure) is expected to have a higher completeness rate of over 90%.

By assessing the primary outcome parameter, the study aims to determine whether the FlowSure device significantly improves the completeness of hourly urine production registration, as compared to the manual urine monitor. The primary outcome will provide crucial insights into the devices' ability to accurately capture and register hourly urine production data, which is vital for monitoring and managing various clinical conditions.

The completeness of hourly urine production registration serves as a key indicator of the devices' reliability, usability, and potential clinical utility and safety. The primary outcome parameter will be analysed statistically, as described earlier, to assess the significance of the observed difference in completeness rates between the two devices.

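### Section 9's only planned analysis, a two-group test of completeness proportions, cannot address Part A's primary outcome of volume accuracy in one group of 25 patients

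*Combined protocol and SAP*

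**What the plan says.** Part A has its own objective, design and outcome.

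- Section 2 gives its objective as "to demonstrate that in clinical care the investigational FlowSure device is able to monitor urine production accurately and safely".
- Section 3 gives its design: "Part A is single arm intervention study in which patients will receive both the manual monitors and automated FlowSure monitor".
- Section 7.1.1 gives its outcome: "The primary outcome event in Part A will be the accuracy of urine measurement over two set time intervals", namely an 8-hour nursing shift and a full 24 hours. It names the reference: "The golden standard is the total urine production measured in a measuring cup by draining the collection bag". The Summary adds that the manual and the automated readings are both compared with that reference.
- Section 4.3 sets 25 patients, without a calculation.

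Section 9 does not follow this structure.

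- Section 9.1 opens: "To analyse the data, a two-group comparison of proportions will be performed using appropriate statistical tests", with chi-square and Fisher's exact test as examples. Its null hypothesis "assumes no difference in completeness rates between the manual urine monitor and the FlowSure device". Its exploratory analyses "may be conducted to investigate potential factors influencing completeness rates and to account for confounding variables".
- Section 9.2 states: "The primary outcome parameter of this study is the completeness of hourly urine production registration". In section 7.1.1 this is the outcome of Part B only.

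Two numerical limits on device performance appear elsewhere. The structured risk analysis (11.7, item e) allows the move to Part B only if FlowSure is within 15% of manual monitoring. Section 7.6 gives a deviation of more than 20% from the measuring cup as an example of a reason to end the study early.

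**The concern.** A chi-square or Fisher test compares the share of yes/no results in two independent groups. Part A has one group, its data are continuous volumes, and the readings are paired within patients. The stated test has nothing to act on there, and the stated primary parameter is not Part A's.

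If section 9 is followed as written, Part A yields no pre-specified result, although section 2 says that it should demonstrate accuracy. The method would have to be chosen later, possibly with the data in view. The same holds for the 15% threshold: the plan gives the number but not the quantity to set against it. In Part B, FlowSure replaces the manual monitor in half the patients, so the decision that rests on Part A is not a minor one.

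**Working it through.** **Step 1. Match the stated analysis to each part.**

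| | Part A (sections 3, 4.3, 7.1.1, Summary) | Part B (sections 3, 4.3, 7.1.1) | Section 9 analysis |
|---|---|---|---|
| Groups | one, 25 patients | two, 25 each | two |
| Data | volumes from FlowSure, manual monitor and cup | hourly registrations made or missed | proportions |
| Pairing | within patient | none | none |
| Question | error against the cup at 8 h and 24 h | difference in completeness | difference in completeness |

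Section 9 fits the Part B column only. No other section gives an error measure for Part A, an agreement or paired method, a confidence interval, or a way to handle the two time intervals.

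**Step 2. The plan's own figures.** There is no precision or power figure for Part A. The only power figure is about 99% for Part B (section 4.3). It follows from the stated SE of 0.0948: 4.216 − 1.96 = 2.256, which gives 98.8%. The stated proportions with 25 per arm give a pooled SE of √(2 × 0.70 × 0.30 / 25) = 0.130. That is a separate matter, and nothing here rests on it.

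**Step 3. Precision that 25 pairs allow.** With t(0.975; 24 df) = 2.064, and all 25 patients contributing to the interval in question:

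- The 95% CI half-width for the mean percent difference is 2.064 × SD / √25 = 0.413 SD.
- The 95% CI half-width for each limit of agreement is about 2.064 × SD × √(1/25 + 1.96²/48) = 2.064 × SD × √0.1200 = 0.715 SD.

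**Step 4. What the 15% threshold means under three readings.** The documents give no SD for the paired differences, so a range is assumed, with normal differences and no bias. The readings are:

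- the absolute mean difference is below 15%
- both limits of agreement (mean ± 1.96 SD) lie within ±15%
- all 25 patients lie within ±15%, with probability (2Φ(15/SD) − 1)^25.

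The first two come from 100,000 simulated samples of 25.

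| Assumed SD | CI half-width, mean | Limits of agreement | CI half-width, each limit | Pass on mean | Pass on limits | Pass on all 25 |
|---|---|---|---|---|---|---|
| 5% | 2.1 | ±9.8 | 3.6 | about 100% | 99.7% | 93% |
| 8% | 3.3 | ±15.7 | 5.7 | about 100% | 23.6% | 21% |
| 10% | 4.1 | ±19.6 | 7.2 | about 100% | about 2% | 2.8% |
| 15% | 6.2 | ±29.4 | 10.7 | about 100% | <0.1% | <0.1% |

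Half-widths and limits are in percentage points. At an SD of 5% the three readings nearly agree. From 8% upwards, the unstated choice of statistic largely settles the result.

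**The case against.** The best defence is that Part A is early work. Section 4.3 calls it first-in-human and speaks of safety, initial efficacy and further development, so a formal test may not be needed. That part stands: pre-specified descriptive agreement with intervals would be enough. It does not excuse having no method at all, because section 7.1.1 gives Part A a primary outcome and section 2 says it should demonstrate accuracy.

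It could also be said that 9.1 leaves the choice of test open, and that 9.2 speaks of capturing data accurately. The open choice is only among tests for a two-group comparison of proportions. Section 9.2 goes on to define completeness as the share of hourly measurements recorded, so a wrong value that is recorded still counts as complete.

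A reader might infer three stronger points, which the documents do not support.

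- *The move to Part B has no criterion.* It has one, in 11.7 item e. What is missing is the statistic, the time interval and the treatment of uncertainty.
- *The sponsor will decide without regard to uncertainty.* The plan is silent on this, and silence is not a decision to ignore it.
- *15% is the sponsor's limit for error against the cup, so the CI of FlowSure's mean error should lie within ±15%.* The 15% refers to manual monitoring, and the only cup-based figure is the 20% example in section 7.6. Such a rule would be a new criterion. It would also be a weak one, because over- and under-readings cancel in a signed mean. With no bias it passes 99.5% of samples at an assumed SD of 15%, and about 90% at 20%.

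**Conclusion.** The concern holds. Section 9 as written cannot answer Part A's primary question, and no other section fills the gap. This follows from the text alone and needs no assumed SD. It is more than missing detail, because the test and the primary parameter that section 9 assigns to the whole study are the wrong ones for Part A.

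The 15% threshold exists but is not operational, and its comparator differs from the cup used in 7.1.1 and 7.6. The size of that ambiguity does depend on assumptions (normal differences, no bias, SD from 5% to 15%). At an SD of 10%, the chance of passing runs from about 100% on the mean to about 2% on the limits of agreement. If the spread is as small as 5%, the choice matters little. The bench result of within 1% (6.1) was obtained at one fixed pump rate and does not supply a patient-level SD.

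**What to change.** 1. Limit 9.1 and 9.2 to Part B, and describe completeness as the primary outcome of Part B.
2. Add a Part A analysis. For each patient, and separately for the 8-hour and 24-hour intervals, compute percent error against the cup for FlowSure and for the manual monitor. For each monitor, report mean bias and limits of agreement, all with 95% CIs. Compare the monitors by the paired difference in absolute percent error, with a 95% CI.
3. Reconcile 11.7 item e with 7.1.1 and 7.6. Before Part A is analysed, state which statistic, time interval and comparator the 15% applies to, and how uncertainty enters the decision. The choice is the sponsor's.

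The cost is a short addition to section 9 and a little more analysis, using volumes that Part A already plans to collect. The drawback is that the intervals will be wide with 25 patients: about ±4 points for the mean and ±7 points for each limit of agreement at an assumed SD of 10%. The report will have to show this openly.

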### 4.3 Sample size calculation

Part A will consist of 25 patients. Since this is the first-in-human study, to establish safety, and initial efficacy the investigators believe that this number will provide us meaningful information to collect scientific data for further development.

Part B will consist of 25 patients monitored with a manual monitor and 25 patients monitored with the FlowSure. The completeness of hourly urine production registration between the manual urine monitor and the FlowSure was compared using a two-group comparison of proportions. The study enrolled a total of 50 patients, with 25 patients using the manual urine monitor and 25 patients using the FlowSure. The completeness rate for the manual urine monitor was approximately 50% ( $P_1 = 0.50$ ), while the FlowSure data collection demonstrated a higher completeness rate of >90% ( $P_2 = 0.90$ ).

To assess the statistical significance of the difference in completeness rates, a significance level (alpha) of 0.05 was employed. The power (1 - beta) was set at 0.8. The pooled proportion (P) was calculated to be 0.70, and the standard error (SE) was estimated as 0.0948. Using a z-score of 1.96 for the selected alpha level, the difference in completeness rates was determined to be 0.40.

The effect size (ES), calculated by dividing the difference in completeness rates by the standard error, was found to be 4.216. Consequently, the study had a power of approximately 99% to detect the assumed difference in completeness rates between the manual urine monitor and the FlowSure monitoring device.

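### The Part B primary analysis does not say whether the hour or the patient is tested, and its named tests do not work as written on either reading

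*Combined protocol and SAP*

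**What the plan says.** Section 9.1 states that "a two-group comparison of proportions will be performed using appropriate statistical tests, such as the chi-square test", with Fisher's exact test as the other example. Regression modelling appears there only as an optional exploratory analysis of influencing factors and confounding.

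Section 9.2 defines the endpoint: completeness "represents the proportion or percentage of the total hourly measurements that are successfully recorded by each device". Its illustration lies within one patient: "if a patient's urine output is measured every hour for 24 hours, the completeness rate indicates how many of these hourly measurements are successfully captured". For the analysis, 9.2 refers back to 9.1 and adds no unit, cut-off or correlation model.

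Two other places bear on the unit, and they point in different directions. Section 9.2 treats the control rate as a share of hours: "The manual urine monitor has an assumed completeness rate of approximately 50% of hourly registrations". Section 4.3 puts the same 50%, with 90% for FlowSure, into a calculation based on patients: "The study enrolled a total of 50 patients, with 25 patients using the manual urine monitor and 25 patients using the FlowSure".

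The number of hours also varies between patients. Under section 3, "the study will last for duration that the patient has a urine catheter inserted with a maximum of 24 hours".

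**The concern.** Chi-square and Fisher's exact tests compare counts of independent yes/no results. The endpoint in 9.2 is a per-patient fraction, so something has to be done before either test can be applied, and the plan does not say what.

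- **Hours as the unit.** Each hour is recorded or not, so the form fits. But hours from one patient share the same ward, nurses and device, so they are unlikely to be independent. No adjustment for this is planned.
- **Patients as the unit.** Independence is reasonable, but each patient then needs a yes/no result. No threshold for a complete patient is given anywhere.

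Part B is not blinded, and the unit and threshold stay open until the data are in. At stake are the false-positive rate, the width of any interval reported, and the size of the reported difference.

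**Working it through.** **Inputs.** 25 patients per arm, 0.50 versus 0.90, alpha 0.05 and z = 1.96 (section 4.3); at most 24 hours per patient (sections 3 and 9.2). The documents give no ICC, so a range is used. Simulations and cut-off probabilities assume a beta-binomial model for hours within patients.

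**1. Does the plan's own calculation reveal the unit?** Section 4.3 states SE 0.0948, effect size 4.216 and power of about 99%.
- From the stated SE: 0.40/0.0948 = 4.22 and Φ(4.22 − 1.96) ≈ 0.99.
- With 25 patients per arm: SE = √(0.70 × 0.30 × 2/25) = 0.1296 pooled, or √((0.25 + 0.09)/25) = 0.1166 unpooled. Power is about 0.89 by the usual two-sided formula and 0.83 for exact Fisher.
- With pooled hours (25 × 24 = 600 per arm): SE = √(0.21 × 2/600) = 0.0265.

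The stated SE matches neither unit, so it does not settle the question. The mismatch is a separate error.

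**2. Pooled hours, no true difference.** With m hours per patient the variance is inflated by 1 + (m − 1) × ICC, and the actual error is 2 × [1 − Φ(1.96/√(1 + (m − 1) × ICC))]. Example for m = 24, ICC 0.05: 1 + 23 × 0.05 = 2.15; 1.96/√2.15 = 1.34; error 0.18.

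| ICC | 24 h per patient | 8 h per patient | 6–24 h (assumed uniform) |
|---|---|---|---|
| 0.01 | 7.7% | 5.8% | 7% |
| 0.05 | 18% | 9.2% | 14% |
| 0.10 | 28% | 13% | 22–23% |
| 0.30 | 49% | 27% | 42% |

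Simulation agrees with the formula to within about one percentage point.

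**3. Pooled hours at the planned effect.** z = 0.40/0.0265 = 15.1. At ICC 0.5 the inflation is 1 + 23 × 0.5 = 12.5, so z falls to 15.1/√12.5 = 4.3, which is still clearly significant. The interval fares worse: a nominal 95% interval from pooled hours covers the true difference about 92%, 82%, 72% and 51% of the time at ICC 0.01, 0.05, 0.10 and 0.30.

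**4. Patients as the unit, Fisher's exact test, ICC 0.05.** The table gives the probability that a patient reaches the cut-off, then exact power with 25 per arm.

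| Cut-off (hours of 24) | Manual | FlowSure | Difference | Power |
|---|---|---|---|---|
| ≥12 | 55.3% | 99.9% | 45 points | 0.99 |
| ≥20 | 1.6% | 84.4% | 83 points | about 1.00 |
| ≥22 | 0.2% | 60.4% | 60 points | about 1.00 |
| ≥23 | 0.0% | 41.5% | 41 points | 0.98 |
| 24 | 0.0% | 19.4% | 19 points | 0.36 |

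At the 24-hour cut-off, power is 0.04, 0.77 and 0.99 at ICC 0.01, 0.10 and 0.30.

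**5. Patient percentages compared by Welch t-test.**
- Null rejection is 0.043–0.052 with 24 hours per patient and 0.044–0.052 with stays of 6–24 hours.
- At 50% versus 90%, interval coverage is about 95% and power is at least 0.99 for ICC up to 0.5.
- The mean half-width at ICC 0.05 is 0.070, against 0.047 from pooled hours.

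**The case against.** The best defence is that 9.1 offers its tests only as examples of appropriate ones. It commits to neither chi-square nor pooling, and 4.3 suggests patients. The type I error figures apply only if hours are pooled, assume no true difference, and rest on an ICC range that the documents do not anchor. At the planned effect the conclusion is safe under pooling, and among patient-level cut-offs only 24 of 24 loses material power. Even 23 of 24 gives 0.87 at ICC 0.01 and at least 0.98 at ICC 0.05 to 0.30. Section 9.1 also promises a p-value, not an interval.

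Much of this stands. The plan is under-specified rather than committed to a wrong analysis, and low power is not the main danger. But leaving the test open is itself the gap in a primary analysis, and reading 4.3 as patient-based only makes the missing cut-off essential. Where power is safe, the reported difference still ranges from about 41 to 83 points with the cut-off. The 50% and 90% are assumptions, and a smaller true difference would remove the protection they give. An interval will probably be wanted, because section 11.1 foresees sharing the data for device certification.

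Welch is one sound choice among several; Mann–Whitney behaves similarly in the simulations. Whether a value read by eye from the bag counts as a FlowSure registration, and how replacement of patients under 7.4 is handled, are separate questions that the choice of unit does not answer.

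**Conclusion.** The concern holds and should be fixed. The tests named in 9.1 cannot be applied to the endpoint in 9.2 without a decision that the plan does not make: pooling hours breaks independence, and testing patients lacks a definition of success. Under pooling with 24 hours each, the true error is roughly 8% to 49% for ICC 0.01 to 0.30, and the interval covers about 92% down to 51%. With patient cut-offs, the reported difference depends on the threshold, and power collapses only for the all-24-hours rule at lower ICC. At 50% versus 90% the finding of a difference would very probably stand. That the unit and cut-off are missing is plain from the text. The sizes depend on the assumed ICC and the beta-binomial model.

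**What to change.** In sections 9.1 and 9.2:

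- Name the patient as the unit of analysis.
- Define each patient's completeness as hours with a registered value divided by hours observed with the catheter in place, up to 24.
- Replace chi-square/Fisher with one prespecified primary test: a two-sided Welch t-test on the patient percentages, reporting the mean difference with its 95% confidence interval.
- Keep a Wilcoxon rank-sum test, or a logistic GEE clustered on patient with small-sample correction, as sensitivity analysis only.
- State that every patient counts equally whatever the length of observation. This is a choice of estimand and should be made openly.

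The cost is a few sentences, with no extra patients or data. The interval will be about 1.1 to 3.7 times as wide as pooled hours would give for ICC 0.01 to 0.5, because the pooled interval is too narrow. Patients observed briefly count as much as those observed for 24 hours. Welch becomes conservative if both arms are nearly complete: with both averaging 95–97%, null rejection was between 0.011 and 0.049, which is far from the planned scenario.
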